4.2 Secondary Endpoint(s)

4.2.1 Progression Free Survival Based on BICR Assessment

PFS is defined as the time from first dosing date to the date of the first documented progression using the IPCG Criteria for PCNSL and Lugano 2014 response evaluation for PTL, as determined by BICR, or death due to any cause, whichever occurs first. Participants who die without a reported progression and did not start a subsequent therapy will be considered to have progressed on the date of their death. Participants who did not progress or die will be censored on the date of their last tumor assessment. Participants who did not have any on study assessments and did not die will be censored on the first dosing date. Participants who started any subsequent anti-cancer therapy without a prior reported progression will be censored at the last tumor assessment prior to initiation of the subsequent anti-cancer therapy.

The censoring scheme is summarized in [Table 4.2.1-1](#).

Table 4.2.1-1: Censoring scheme used in primary analysis of PFS

Situation	Date of Progression or Censoring	Outcome
No baseline tumor assessments and no death	First dosing date	Censored
No on-study tumor assessments and no death	First dosing date	Censored
New subsequent anticancer therapy started without a prior reported progression by IPCG/Lugano 2014 criteria	Date of last evaluable tumor assessment prior to or on the date of initiation of the subsequent anti-cancer therapy	Censored
Progression per IPCG / Lugano 2014 criteria documented at a scheduled or unscheduled visit and no subsequent anticancer therapy started before	Date of the first documented tumor progression per IPCG/Lugano 2014 criteria	Progressed

Table 4.2.1-1: Censoring scheme used in primary analysis of PFS

Situation	Date of Progression or Censoring	Outcome
Participant progression free, no death and no subsequent anti-cancer therapy started	Date of last evaluable tumor assessment per IPCG/Lugano 2014 criteria	Censored
Death without prior progression per IPCG/Lugano 2014 criteria and no subsequent anticancer therapy started	Date of death	Progressed

4.2.2 *Objective Response Rate and Duration of Response Based on Investigator Assessment*

Investigator-assessed ORR and DOR are defined similarly as described for ORR and DOR per BICR assessment above, but will be assessed per investigator.

4.2.3 *Overall Survival*

Overall Survival (OS): defined as the time between the first dosing date and the date of death. Participants who are alive at the time of analysis will be censored at last known alive date (LKAD). The overall survival rate at time T is defined as the probability that a subject is alive at time T following first dosing date.

5 SAMPLE SIZE AND POWER

The planned sample size for this study will be approximately 65 treated participants, placed into 2 cohorts of participants: PCNSL (N = 45), and PTL (N = 20).

In addition, [Table 5-1](#) summarizes the 95% exact confidence interval (CI) for the target ORRs ranging from 28.9% to 60% with sample size of 20 and 45. At observed ORR \geq 28.9% with 45 PCNSL participants, the lower bound of the 95% CI excludes the historical response rates in of 14% in recurrent primary central nervous system lymphoma. At observed ORR \geq 40% with 20 PTL participants, the lower bound of the 95% CI excludes the response rate of 14%.

The sample size for the PCNSL cohort was empirically determined to support expanded assessment of the benefit-risk profile of nivolumab in PCNSL through observation of less common safety events. In particular, administration of nivolumab to 45 participants provides 90% probability of observing at least 1 occurrence of any AE that would occur with 5% incidence in the population from which the sample is drawn.

Table 5-1: Observed ORR with Exact 95 % CI

N	ORR	95% Exact CI
20	30%	[11.9% - 54.3%]
	35%	[15.4% - 59.2%]
	40%	[19.1% - 63.9%]
	50%	[27.2% - 72.8%]
	60%	[36.1% - 80.9%]
45	28.9%	[16.4% - 44.3%]
	40.0%	[25.7% - 55.7%]
	51.1%	[35.8% - 66.3%]
	60%	[44.3% - 74.3%]

6 STUDY PERIODS, TREATMENT REGIMENS AND POPULATIONS FOR ANALYSES

6.1 Study Periods

6.1.1 *Baseline Period*

Baseline evaluations or events will be defined as evaluations or events that occur before the date and time of the first dose of study treatment.

In cases where the time (onset time of event or evaluation time and dosing time) is missing or not collected, the following definitions will apply:

- Pre-treatment AEs will be defined as AEs with an onset date prior to but not including the day of the first dose of study treatment

- Baseline evaluations (laboratory tests, pulse oximetry and vital signs) will be defined as evaluations with a date on or prior to the day of first dose of study treatment.

If there are multiple valid assessments, the assessment that is closest to day (and time if collected) of the first dose of study treatment will be used as the baseline in the analyses. If multiple assessments are collected at the same date (and time if collected), the assessment with the latest database entry date (and time if collected) will be considered as baseline.

6.1.2 Post Baseline Period

On-treatment AEs will be defined as AEs with an onset date-time on or after the date-time of the first dose of study treatment (or with an onset date on or after the day of first dose of study treatment if time is not collected or is missing). An AE will be counted as on-treatment if the event occurred within 30 days (or 100 days depending on analysis) of the last dose of study treatment.

On-treatment evaluations (laboratory tests, pulse oximetry and vital signs) will be defined as evaluations taken after the day (and time, if collected and not missing) of first dose of study treatment. An evaluation will be counted as on-treatment if it occurred within 30 days (or 100 days depending on analysis) of the last dose of study treatment.

See Core Safety SAP.

6.2 Treatment Regimens

All participants will be treated with nivolumab 240 mg, given every 2 weeks for 8 cycles. Beginning with Cycle 9, nivolumab 480 mg will be given every 4 weeks for a total therapy duration of 2 years, or until progressive disease, unacceptable toxicity, or withdrawal of consent.

6.3 Populations for Analyses

Within each cohort the following populations will be defined.

- **All enrolled participants:** All participants who signed an informed consent form and were registered into the IVRS.
- **All treated participants:** All participants who received at least one dose of study medication. This is the primary dataset for efficacy and safety.
- **All treated participants enrolled pre-amendment 9:** All treated participants who signed their informed consent before protocol amendment 9 (up to March 24, 2017).
- **All treated participants enrolled post-amendment 9:** All treated participants who signed their informed consent after protocol amendment 9 (after March 24, 2017).
- All treated participants with high dose corticosteroids at baseline: All treated participants who received > 2 mg per day of dexamethasone equivalent within 14 days prior first Nivolumab dose date.
- All treated participants without high dose corticosteroids at baseline: All treated participants who received ≤ 2 mg per day of dexamethasone equivalent within 14 days prior first Nivolumab dose date.

- **Response evaluable participants:** All treated participants who have baseline and at least one on-study evaluable tumor measurement.
[REDACTED]
[REDACTED]
- **Serum PK participants:** All participants with available serum concentration time data from participants dosed with nivolumab
- **CSF PK participants:** All participants with available CSF concentration time data from participants dosed with nivolumab
- **Immunogenicity evaluable participants:** All treated participants with baseline and at least 1 post baseline immunogenicity assessment
- **Outcomes research participants:** All treated participants who have an assessment at baseline (Visit 1 assessment prior to administration of drug) and at least 1 subsequent assessment (separately for each outcome research measure EuroQol (EQ)-5D-3L scoring function, QLQ-C30, QLQ-BN20 and NANO).
- **Nivolumab participants treated beyond progression:** All participants who received at least one dose of nivolumab after the date of initial progression based on investigator assessment.

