Amendment 01	22-Jun-2016	
• Subjects in the cohorts with PCNSL and PTL with brain and/or spinal lesions are allowed to enroll if they are on 4 mg per day or less of dexamethasone.• Subjects who had undergone allogeneic stem cell transplant > 12 months prior to first dose of study drug, have no evidence of active graft versus host disease, and are not on systemic immunosuppressive therapy are allowed to participate in the study.• Neurologic Assessment in Neuro-Oncology (NANO) has been incorporated in the exploratory endpoints in the protocol.• If the dose of dexamethasone is increased during the screening period following the screening MRI, and if there is clinical worsening in neurological symptoms following the MRI, the MRI must be repeated.• Due to the rapidly progressing nature of CNS tumors, a brain MRI is to be performed within 14 days before the first dose of study treatment in both cohorts in order to accurately reflect the disease burden.• Language was added for the collection of prospective blood samples, and for BMS to retain residual blood and tissue samples, so that scientists can perform additional research.• Incorporation of other minor changes to correct and/or clarify protocol requirements.
Original Protocol	13-Apr-2016	Not applicable

OVERALL RATIONALE FOR THE REVISED PROTOCOL 04

Revised Protocol 04 incorporates changes that will allow for the characterization of nivolumab pharmacokinetics (PK) in paired cerebrospinal fluid (CSF) and blood samples, [REDACTED] in the CSF of patients with relapsed/refractory PCNSL or relapsed/refractory PTL with central nervous system (CNS) involvement, who consent for lumbar puncture. The collection of CSF is an optional assessment; consent for the lumbar puncture is required.

[REDACTED]

All revisions apply to future and currently enrolled patients.

SUMMARY OF KEY CHANGES OF REVISED PROTOCOL 04

Section Number & Title	Description of Change	Brief Rationale
[REDACTED]	[REDACTED]	[REDACTED]

Section 5.1, Flow Chart/Time and Events Schedule Table 5.1-2. CSF assessment note	
The note for the CSF on-treatment assessment was revised to include text for collection of CSF for nivolumab PK and select biomarkers, and paired blood samples for PK (optional consent required).[REDACTED]	[REDACTED]

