3.3.2 Exclusion Criteria

1. Target Disease Exceptions

- a) Intraocular PCNSL without evidence of brain disease. Patients with prior history of intraocular involvement treated only with intraocular methotrexate and no prior systemic therapy are excluded.
- b) PCNSL patients who cannot undergo MRI with contrast assessments
- c) PCNSL patients with systemic disease
- d) Patients with brain stem lesions

2. Medical History and Concurrent Diseases

- a) Subjects with an active, known, or suspected autoimmune disease. Subjects with type I diabetes mellitus, hypothyroidism only requiring hormone replacement, skin disorders (such as vitiligo, psoriasis, or alopecia) not requiring systemic treatment, or conditions not expected to recur in the absence of an external trigger are permitted to enroll.
- b) Subjects with a condition requiring systemic treatment with either corticosteroids (> 10 mg daily prednisone equivalent) or other immunosuppressive medications within 14 days of start of study treatment. Inhaled or topical steroids, and adrenal replacement steroid doses > 10 mg daily prednisone equivalent, are permitted in the absence of active autoimmune disease. ^{65,66}

For subjects with PCNSL and PTL with brain or spinal cord lesion: Subjects who have received 2 mg/day or less of dexamethasone equivalent in the 14 days prior to the first nivolumab dose are eligible for the study. Documentation that the dose has been stable or decreased for at least 14 days prior to the first dose of nivolumab is required. Subjects who have received doses of more than 2 mg/day of dexamethasone or equivalent within the 14 days period prior to the first dose of nivolumab are excluded.

NOTE: During study treatment, subjects may be treated with steroids including bolus doses for IMAEs or tumor flare detailed in [Appendix 5](#) and [Appendix 6](#), respectively, and in [Sections 3.4.1](#) and [3.4.2](#).

- c) Subjects who have received chemotherapy within 3 weeks of study treatment (except: HD-MTX within 2 weeks of treatment permitted if serum MTX levels < 1 μ M and meets other

lab criteria for inclusion), nitrosoureas within 6 weeks of treatment, therapeutic anti-cancer antibodies (such as rituximab) within 4 weeks, radio- or toxin immune-conjugates within 10 weeks of treatment.

- d) Received any investigational agent within 28 days or 5 half-lives (whichever is longer) prior to initiation of study treatment

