2.4 Protocol Amendments

Table 2.4-1: Protocol Amendments

Document	Date of Issue	Summary of Change
Revised Protocol 04	29-Nov-2017	To characterize nivolumab pharmacokinetic [REDACTED] in the cerebrospinal fluid (CSF), lumbar puncture(s) (optional) have been added and will be obtained from consenting patients with relapsed/refractory PCNSL or relapsed/refractory PTL with CNS involvement. [REDACTED]
Administrative Letter 06	04-Sep-2017	Corrected the Appendix 6 of the protocol (Tumor Flare; Treatment strategies during TF) by removing the CTCAE classification of cerebral edema.
Revised Protocol 03	07-Apr-2017	Incorporates Amendment(s) 09 Changes to eligibility - To allow enrollment of subjects with PTL who undergo orchiectomy - To allow enrollment of subjects with PTL with measurable nodule disease - To specify more precisely the first line of therapy in PCNSL and PTL - To exclude subjects with significantly increased risk for bleeding complications - To lower the dose of dexamethasone or equivalent allowed 14 days prior to first dose of nivolumab to less than or equal to 2mg/day. The use of CT Scans without PET scans will not be allowed for assessment for subjects with PTL. Added the possibility for administrative interim analyses. Recommendations for the management of Tumor Flare have been added as Appendix 6.
Amendment 09	07-Apr-2017	Incorporates changes per Administrative Letters 04, 03, and 02.
Administrative Letter 04	07-Feb-2017	Change Medical Monitor address.
Administrative Letter 03	17-Nov-2016	To further clarify protocol requirements for tumor tissue submission at screening and correct typographic errors in Table 5.1-2 of the protocol.
Administrative Letter 02	20-Oct-2016	Clarify the protocol requirements for tumor tissue submission at screening.
Revised Protocol 02	05-Oct-2016	Incorporates Amendment(s) 05
Amendment 05	05-Oct-2016	To reflect update in the treatment management algorithms to be consistent with the updated nivolumab investigator brochure (IB) V15, updates to the acceptable methods of contraception in order to be consistent with the most recent version of BMS SOP and IB V15. To allow the enrollment of patients with PCNSL that cannot produce a minimum of 25 slides [REDACTED]

Table 2.4-1: Protocol Amendments

Document	Date of Issue	Summary of Change
		Other changes were made to resolve minor inconsistencies or to provide clarifications.

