7.5.2.5 Efficacy for Participants Treated Beyond Progression

Individual time course of tumor burden change from baseline in target lesions, per investigator, will be generated for nivolumab participants treated beyond progression (spider plot).

The duration of treatment and number of doses beyond progression will be summarized.

7.5.3 *Subset Analyses*

The influence of enrolment prior versus after protocol amendment 9 and the influence on high versus lowdose of dexamethasone prior to the first dose of nivolumab on the efficacy measures will be evaluated descriptively by analyzing the following efficacy endpoints on each subset:

- BICR-assessed best overall response (BOR) will be summarized by response category (CR, CRu, PR, SD, PD, Non-evaluable, and not reported).
- BICR-assessed time to response (TTR) will be analyzed using the KM methodology.
- BICR-assessed DOR will be summarized for participants who achieve PR, CRu or CR using the Kaplan-Meier product-limit method. Median values of DOR, along with two-sided 95% CIs (based on the log-log transformation) and range, will also be calculated.
- The BICR-assessed PFS assessment will be summarized descriptively using the Kaplan-Meier (KM) product-limit method. Median values of PFS, along with two-sided 95% CIs (based on the log-log transformation), will also be calculated.
- The OS curves will be estimated using the Kaplan-Meier (KM) product-limit method. Two-sided, 95% confidence intervals for median OS will be constructed based on a log-log transformed CI for the survivor function $S(t)$.

To study the effect of steroid use at baseline, objective response status (responder vs non-responder) may be modeled by a logistic regression with baseline steroid use as a continuous variable. For PFS and OS, a Cox proportional hazards model with baseline steroid use as a continuous variable may be applied.

7.5.4 *Interim Analysis*

Not applicable.

7.6 *Safety*

A subset of tables and listings from the Core Safety SAP will be analyzed. Details will be included in the DPP.

7.6.1 *Deaths*

See Core Safety SAP.

7.6.2 *Serious Adverse Events*

See Core Safety SAP.

7.6.3 *Adverse Events Leading to Discontinuation of Study Therapy*

See Core Safety SAP.

7.6.4 *Adverse Events Leading to Dose Modification*

See Core Safety SAP.

7.6.5 *Adverse Events*

See Core Safety SAP.

7.6.6 *Select Adverse Events*

See Core Safety SAP.

7.6.7 *Immune Modulating Medication*

See Core Safety SAP.

7.6.8 *Multiple Events*

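### The high- versus low-steroid comparison in SAP 7.5.3 is partly confounded with enrolment before or after Amendment 9, and the two steroid sets need one exclusive classification rule

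*SAP*

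**What the plan says.** **Steroid sets.** SAP 6.3 defines the high set as "All treated participants who received > 2 mg per day of dexamethasone equivalent within 14 days prior first Nivolumab dose date" and the low set as "All treated participants who received ≤ 2 mg per day of dexamethasone equivalent within 14 days prior first Nivolumab dose date". The low set is headed "All treated participants without high dose corticosteroids at baseline". No rule is given for a dose that changes within the window.

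**Period sets.** SAP 6.3 also splits treated participants by consent up to, or after, 24 March 2017, and labels these sets pre- and post-amendment 9. The protocol's document history dates Amendment 9 to 7 April 2017.

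**Entry limits.** The document history records that under Amendment 01 subjects in both cohorts with brain or spinal lesions "are allowed to enroll if they are on 4 mg per day or less of dexamethasone". Current Protocol 3.3.2, criterion 2b, excludes PCNSL subjects, and PTL subjects with brain or spinal cord lesions, who had more than 2 mg/day in the 14 days before first dose. It adds: "Documentation that the dose has been stable or decreased for at least 14 days prior to the first dose of nivolumab is required".

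**Other changes in Amendment 9.** SAP Table 2.4-1 lists, besides the steroid limit, "To exclude subjects with significantly increased risk for bleeding complications", a more precise statement of first-line therapy, and two changes to PTL eligibility.

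**Planned analysis.** SAP 7.5.3 will evaluate descriptively "The influence of enrolment prior versus after protocol amendment 9 and the influence on high versus lowdose of dexamethasone prior to the first dose of" study treatment, with BOR, TTR, DOR, PFS and OS reported on each subset. It adds that "objective response status (responder vs non-responder) may be modeled by a logistic regression with baseline steroid use as a continuous variable", and allows a Cox model of the same form for PFS and OS.

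**The concern.** The steroid cut and the new entry limit are the same number over the same window. The rule that removed high-dose subjects from later enrolment therefore ties high dose to the earlier period. The low set does not have that tie, because it takes low-dose participants from both periods.

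High versus low then compares a nearly all-early group with a mixed group. Any change in response caused by the amendment's other eligibility rules, or by anything else that shifted over time, enters the difference and would be reported under the heading of steroid influence. The optional models do not remove this, because period is not among their stated terms.

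At stake is what the report says about baseline corticosteroid and nivolumab activity, a question the SAP poses itself. A secondary issue is that both set definitions ask what was received within the window. Read literally, a participant whose dose fell from above 2 mg/day to 2 mg/day or below in those 14 days meets both.

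**Working it through.** The plan states no subset size, power or effect for this comparison, so there is no figure of its own to reproduce. The check has a logical part, from the documents, and an illustrative part, with assumed inputs.

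**1. Who can be in each cell (from the documents)**

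| | Consent up to 24 March 2017 | Consent after 24 March 2017 |
|---|---|---|
| > 2 mg/day | allowed by the 4 mg/day limit | only by deviation (foreseen in SAP 7.2.2), or while a site was still under the earlier limit |
| ≤ 2 mg/day | allowed | allowed |

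The gap between cut date and amendment date is 24 March to 7 April, which is 14 days. Someone who consented in it is labelled post-amendment although the 2 mg/day rule had not been issued.

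**2. Size of a false steroid effect (illustration)**

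The documents supply PCNSL N = 45 (SAP section 5). Assumed: the number enrolled pre-amendment, how many of them were high-dose, the ORR in each period, and no steroid effect at all.

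With every high-dose participant pre-amendment, ORR(high) = ORR(pre), and

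ORR(low) = [n(low, pre) × ORR(pre) + n(post) × ORR(post)] / n(low).

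So high − low = −(post-amendment share of the low set) × [ORR(post) − ORR(pre)].

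Middle case: 22 pre-amendment (11 high, 11 low), 23 post, ORR 20% then 40%. ORR(low) = (11 × 0.20 + 23 × 0.40)/34 = 11.4/34 = 33.5%. High − low = 20.0 − 33.5 = −13.5 points.

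| Pre-amendment n | High | Low (pre + post) | Post share of low | False difference, ORR 20% then 40% | False difference, ORR 30% then 40% |
|---|---|---|---|---|---|
| 15 | 10 | 5 + 30 = 35 | 86% | −17.1 | −8.6 |
| 22 | 11 | 11 + 23 = 34 | 68% | −13.5 | −6.8 |
| 30 | 9 | 21 + 15 = 36 | 42% | −8.3 | −4.2 |

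The sign follows the assumption that response rose after the amendment. If it fell, the sign reverses. If it did not change, the bias is zero.

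**3. Effect of some high-dose participants being labelled post-amendment (middle case)**

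- 0 such participants: −13.5 points.
- 2: high (2.2 + 0.8)/13 = 23.1%, low (2.2 + 8.4)/32 = 33.1%, difference −10.0.
- 4: high (2.2 + 1.6)/15 = 25.3%, low (2.2 + 7.6)/30 = 32.7%, difference −7.3.

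The bias shrinks but does not vanish.

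**4. Restricting to pre-amendment participants**

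Both groups then have ORR(pre), so the false difference is 20% − 20% = 0. The price is precision. With 11 per group, power for 20% versus 50% (normal approximation, two-sided 5%) comes from z = (0.30 − 1.96 × √(2 × 0.35 × 0.65/11)) / √((0.16 + 0.25)/11) = (0.30 − 0.399)/0.193 = −0.51, which is about 30%. Four responders out of 11 would carry an exact 95% interval of 10.9% to 69.2%.

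**5. Overlap**

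If 3 to 5 participants tapered across 2 mg/day and were counted under both definitions, the set sizes in the middle case would add to 11 + 34 + 3 = 48 up to 11 + 34 + 5 = 50, for 45 participants.

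**The case against.** The sponsor can fairly say the following.

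- **The high set is not exclusively pre-amendment.** A reader might infer that high-dose participants can only come from before Amendment 9. The documents do not support that. SAP 7.2.2 lists more than 2 mg/day after the amendment as a deviation, and the 14-day date gap can place eligible high-dose participants in the post set. Protocol 9.1.1 requires ethics approval before a change is implemented, which could lengthen that gap at some sites. This stands, and step 3 shows it reduces the confounding without removing it.
- **The confounding is partial.** Low-dose participants exist in both periods, both factors are already defined in SAP 6.3, and the continuous models also use variation at or below 2 mg/day. This stands. The within-period comparison is possible; it is simply not planned.
- **Pre versus post is not faulty.** Its stated target is the amendment as a whole, and the steroid limit is one part of that package. This stands.
- **The overlap is mainly wording.** The headings, with and without high dose, are complements, and nothing plans to count anyone twice. The stable-or-decreasing sentence is current text, under which anyone above 2 mg/day in the window is excluded, so it does not show that such tapers were allowed before the amendment. The full earlier criterion is not in the documents. This stands, but a classification rule is still missing.
- **The other PCNSL-relevant changes may matter little.** They are a bleeding-risk exclusion and a more precise description of first-line therapy; the rest concern PTL. A rise in ORR from 20% to 40% through these is an assumption only. This stands for the size of the bias, not for its mechanism.
- **Imbalance will be visible.** SAP 7.3.2 tabulates baseline characteristics pre versus post (PCNSL) and by steroid dose. This helps a reader notice a difference but does not separate the two factors.

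**Conclusion.** The point holds in a limited form. By the documents' own eligibility rules, high dose is tied to the pre-amendment period apart from deviations and the date gap, and no stated steroid analysis accounts for period. High versus low, and the steroid-only models, therefore partly confound dose with period and with the other eligibility changes.

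Two stronger conclusions would be wrong: that no steroid effect could be read from this trial's data at all, and that the primary result is compromised. A within-period reading is available from populations already defined, and the primary ORR in all treated participants does not use these sets.

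The size is unknown. The range of 4 to 17 points rests wholly on assumed splits (15 to 30 of 45 pre-amendment, about 30% to 70% of them high-dose), assumed ORRs of 20% or 30% before and 40% after, and no steroid effect. The analysis is descriptive and the models are optional, which limits the consequence. It is still worth correcting, because a table presented as the influence of steroid dose will be read that way.

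**What to change.** **SAP 7.5.3.**
- Keep both planned splits.
- Add a descriptive comparison of high versus low within pre-amendment participants and name it as the main reading of the steroid effect.
- Add pre-amendment low versus post-amendment low, as the amendment comparison among low-dose participants.
- Show any post-amendment high-dose participants as a separate group, so that everyone is accounted for.
- If the logistic or Cox models are run, add a sensitivity version restricted to pre-amendment participants or with a period term. With few events the period term may be unstable, and the report should say so.

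**SAP 6.3.**
- Classify each participant on the highest daily dexamethasone-equivalent dose in the 14 days before first dose: above 2 mg/day is high, and everything else, including no steroid, is low.
- Reconcile the 24 March 2017 cut with the 7 April 2017 amendment date, so that participants who entered under the earlier limit are neither labelled post-amendment nor flagged as deviators under SAP 7.2.2.

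**Cost.** SAP wording and a small set of added subset tables. The classification uses steroid doses the planned sets already require, and eligibility and treatment are untouched. The downside is small groups and wide intervals (step 4). The change removes confounding with period only. Participants needing more steroid may have had worse disease, and that limitation should be stated beside the table.
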